**7.3.2 Demographics and Other Baseline Characteristics**

The definition of baseline defined in [Section 6.1.1](#) will be applied here, with the exception of Viral Tumor Status among SCCHN subjects. For Viral Tumor Status, if there is a Positive finding in any baseline examination, then the subject's status will be designated as Positive.

**Summary:**

The following subject demographics and baseline characteristics will be summarized by treatment arm and overall using descriptive statistics or frequency statistics.

- Age (in years); age category (<65, ≥65)
- Gender
- Race
- Ethnicity (for US only)
- Height
- Baseline Weight
- Baseline ECOG status
- Disease characteristics
  - For NSCLC (both NSCLC-NAIVE and NSCLC-PROG): stage at initial diagnosis and at study entry, cell type, EGFR mutation status, ALK translocation status, tobacco use status, electronic cigarette use status, PD-L1 level
  - For MEL: stage and M status at initial diagnosis and at study entry, subtype of disease, BRAF mutation status, PD-L1 level
  - For SCCHN: stage at initial diagnosis and at study entry, cell type, location, viral tumor status
  - For DLBCL and FL: stage at initial diagnosis and at study entry, IPI score
  - For tumor types that are not NSCLC-NAIVE, MEL, SCCHN, DLBCL, NSCLC-PROG, and FL, the diagnosis will be presented in a frequency table, along with their stage at study entry

**Listing:**

- All relevant data, generally variables listed above
- General medical history
- Tobacco use, electronic cigarette use, and alcohol use
- Relevant factors
- Potential risk factors
  - For Pulmonary related events
  - For Hepatobiliary related events

**7.4 Extent of Exposure**

The extent of exposure will be characterized according to the number of subjects exposed, the duration of exposure, and the dose to which they were exposed. Analyses in this section will be performed on the population of All Treated Subjects “as treated” as described in [Section 6.2](#).

The urelumab and nivolumab combination will be given on Days 1 and 29 in 8 week cycles for 6 cycles. The cycle start date will correspond to the dosing date. Calculations below excludes the re-treatment period.

### **7.4.1      *Study Therapy***

#### **Summary:**

- Number (%) of treated subjects exposed for specified periods of time such as less than 1 week, 1 week to 1 month, 1 month to 6 months by treatment group.
- Descriptive statistics will be provided by treatment group for the following.
  - Urelumab
    - ◆ Number of doses of Urelumab
    - ◆ Duration of therapy (weeks) of Urelumab = (last dose date - first dose date + 28)/7
    - ◆ Cumulative dose (mg) of Urelumab = the sum of all actual doses that a subject received
    - ◆ Dose intensity (mg/wk) = cumulative dose (mg) / duration of therapy (weeks)
    - ◆ Relative dose intensity (%) = (dose intensity / planned dose)\*100
      - Categories: < 50%; 50 - < 70%; 70 - < 90%; 90 - < 110%;  $\geq$  110%
  - Nivolumab
    - ◆ Number of doses of Nivolumab
    - ◆ Duration of therapy (weeks) of Nivolumab = (last dose date - first dose date + 14)/7
    - ◆ For subjects enrolled prior to Protocol Amendment 03:
      - Cumulative dose (mg/kg) of Nivolumab = the sum of all actual doses that a subject received
      - Dose intensity (mg/kg/wk) = cumulative dose (mg/kg) / duration of therapy (weeks)
    - ◆ For subjects enrolled after Protocol Amendment 03:
      - Cumulative dose (mg) of Nivolumab = the sum of all actual doses that a subject received
      - Dose intensity (mg/wk) = cumulative dose (mg) / duration of therapy (weeks)
    - ◆ Relative dose intensity (%) = (dose intensity / planned dose)\*100
      - Categories: < 50%; 50 - < 70%; 70 - < 90%; 90 - < 110%;  $\geq$  110%

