**Table 4:** **Alternate Treatment Regimens**

Cohort Designation	urelumab	nivolumab a
A b	8 mg IV every 8 weeks	3 mg/kg or 240 mg IV every 2 weeks
B	8 mg IV every 8 weeks	1 mg/kg or 80 mg IV every 2 weeks
C b	3 mg IV every 4 weeks	1 mg/kg or 80 mg IV every 2 weeks
D b	3 mg IV every 8 weeks	3 mg/kg or 240 mg IV every 2 weeks

a Nivolumab 1 mg/kg or 3 mg/kg will be administered for subjects enrolled prior to Revised Protocol 02. Nivolumab 80 mg or 240 mg flat dose administered for subjects enrolled after Revised Protocol 02

b Dosing regimen not applicable following Revised Protocol 03 (Dated 31-Aug-2015)

All available clinical and laboratory data observed during dose escalation will be reviewed to determine the alternative treatment regimen listed in [Table 4](#) to be evaluated. The nature, time of onset, and time to resolution of DLTs observed will be reviewed in the context of the current safety data from the respective urelumab and nivolumab trials. After review of this data, and after consultation between the investigators and the sponsor, the identified alternative treatment regimens may be evaluated.

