**Table 6: Protocol Amendments**

Amendments	Date of Issue	Summary of Major Changes
Amendment 01	09-Jul-2014	Inclusion of pharmacogenetic data collection and statistical analysis
Amendment 02	06-Mar-2015	Updates to the inclusion/exclusion criteria, re-treatment phase, and PK sampling and biomarker assessments.
Amendment 03	29-Jun-2015	Changed Nivolumab dosing from mg/kg to mg flat dosing, updated the duration of therapy for both drugs, updates made to the PK endpoints and analyses.
Amendment 04	30-Aug-2015	Removed randomization and Q8W dosing arms from cohort expansion.
Amendment 05	22-Dec-2015	Added 2 tumor types (NSCLC-PROG and FL).

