#### **4.2.2 Pharmacokinetic Endpoints**

The following PK parameters of urelumab derived from serum concentration time profile of subjects using non-compartmental analysis may be included for urelumab PK analysis, depending on the availability of data.

- Cmax ( $\mu\text{g}/\text{mL}$ ) (maximum concentration)
- Tmax (hr) (time to maximum concentration)
- AUC(0-T) ( $\mu\text{g} \cdot \text{hr}/\text{mL}$ ) (area under the plasma concentration-time curve, 0 to time of last quantifiable concentration)
- AUC(TAU) ( $\mu\text{g} \cdot \text{hr}/\text{mL}$ ) (area under the concentration-time curve in one dosing interval, 0 to 28 days)
- Ctrough (trough concentration)
- Ceoinf (end of infusion concentration)

In addition, the following PK parameters of nivolumab will be calculated at specified visits.

- Ceoinf (end of infusion concentration)
- Ctrough (trough concentration)
- AUC(0-T) ( $\mu\text{g} \cdot \text{hr}/\text{mL}$ )
- AUC(TAU) ( $\mu\text{g} \cdot \text{hr}/\text{mL}$ ) (area under the concentration-time curve in one dosing interval, 0 to 14 days)
- Cmax ( $\mu\text{g}/\text{mL}$ )
- Tmax (hr)

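### A fixed 28-day add-on in the SAP makes urelumab duration 4 weeks short, and dose intensity too high, for any subject dosed every 8 weeks

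*SAP*

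**What the plan says.** SAP 7.4.1 gives one duration formula for urelumab, with no condition on regimen: "Duration of therapy (weeks) of Urelumab = (last dose date - first dose date + 28)/7". Two further quantities are built on it. The first is "Dose intensity (mg/wk) = cumulative dose (mg) / duration of therapy (weeks". The second is "Relative dose intensity (%) = (dose intensity / planned dose", multiplied by 100 and grouped as "Categories: < 50%; 50 - < 70%; 70 - < 90%; 90 - < 110", with a top category of 110% or more. Planned dose is not defined and carries no unit. The matching nivolumab formula adds 14 days.

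SAP Table 4 lists urelumab at "8 mg IV every 8 weeks" in Cohorts A and B and at "3 mg IV every 8 weeks" in Cohort D. SAP 6.2 refers to Tables 2 and 4 for the arms explored and warns that some may be empty. SAP 7.4 runs the exposure analysis on All Treated Subjects, as treated, and SAP 7.4.1 reports it by treatment group. For Amendment 04, SAP Table 6 says: "Removed randomization and Q8W dosing arms from cohort expansion". For urelumab AUC(TAU), SAP 4.2.2 fixes the interval as well: "area under the concentration-time curve in one dosing interval, 0 to 28 days".

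**The concern.** The constant added after the last dose credits the subject with the interval which that dose covers, so it should equal the dosing interval. The SAP follows this rule for nivolumab (14 days, dosing every 2 weeks) and for urelumab every 4 weeks (28 days). It breaks the rule for regimens A, B and D, whose interval is 56 days. Nothing else in the SAP excludes those groups from the exposure analysis or corrects the constant.

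At stake is whether the exposure tables can be read across treatment groups. The 4-week groups would be right and any 8-week group would be wrong by construction. The relative error would be largest in subjects who stopped early. Intra-subject dose escalation is not permitted (Protocol 4.5.4), so a relative dose intensity above 100% in a subject dosed exactly on schedule would be an artifact of the formula.

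**Working it through.** **Inputs.** The formulas are those of SAP 7.4.1. The full treatment period is 48 weeks (SAP 6.1.2), which is 24 nivolumab doses every 2 weeks, 12 urelumab doses every 4 weeks, or 6 every 8 weeks. The 8-week regimens are those of SAP Table 4: 8 mg per 8 weeks is 1 mg/week planned, and 3 mg per 8 weeks is 0.375 mg/week planned.

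**Formula.** For n doses given exactly on schedule at interval t days, duration = ((n − 1) × t + add-on)/7 weeks. Dose intensity = n × dose/duration.

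**Reproducing the 48 weeks.**
- Nivolumab: (23 × 14 + 14)/7 = 48 weeks.
- Urelumab every 4 weeks: (11 × 28 + 28)/7 = 48 weeks. Relative dose intensity against the planned weekly dose is exactly 100%.
- Urelumab every 8 weeks: (5 × 56 + 28)/7 = 44 weeks, not 48.

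**8-week regimens, n on-schedule doses.** The SAP duration is (56(n − 1) + 28)/7 = 8n − 4 weeks. With a 56-day add-on it is 8n weeks. The inflation of dose intensity is 8n/(8n − 4), the same for 8 mg and 3 mg.

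| Doses | SAP duration (weeks) | With 56 days (weeks) | Dose intensity inflated by | Relative dose intensity, weekly denominator |
|---|---|---|---|---|
| 1 | 4 | 8 | 2.00 | 200.0% |
| 2 | 12 | 16 | 1.33 | 133.3% |
| 3 | 20 | 24 | 1.20 | 120.0% |
| 4 | 28 | 32 | 1.14 | 114.3% |
| 5 | 36 | 40 | 1.11 | 111.1% |
| 6 | 44 | 48 | 1.09 | 109.1% |

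The shortfall is 4 weeks once per subject, not per dose, because (56 − 28)/7 = 4. It holds whether or not the subject kept to schedule; the inflation factors in the table hold only for on-schedule dosing. As a share of the true duration it runs from 4/8 = 50% after one dose to 4/48 = 8.3% after six. With the 56-day add-on, relative dose intensity is 100% in every row.

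**Dependence on the denominator.** The last column reads planned dose as mg per week, the only reading whose units match dose intensity. Read as mg per administration, the same formula gives 25% for every on-schedule 4-week subject and 13.6% to 25% for 8-week subjects. The duration and dose intensity columns do not depend on this choice.

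**AUC(TAU).** Protocol 1.4.3.1 gives a half-life of about 5.2 to 5.6 days. Assuming single-exponential decline, the share of AUC beyond day 28 is 2^(−28/5.2) = 2.4% to 2^(−28/5.6) = 3.1%, so about 2–3%.

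**The case against.** The strongest objection is that the effect may be nil. Regimens A, B and D are contingent alternates. SAP 6.1.2 and 7.4 describe 4-week urelumab dosing for everyone, and Protocol Tables 5.1-2 and 5.1-5 schedule urelumab only for Cohorts 1, 2 and C. No passage reports a subject treated every 8 weeks. The document history in the Protocol (Administrative Letter 03 and Amendment 04) and SAP Table 6 record that enrollment into Cohorts A to D was discontinued and that the 8-week arms were removed. This suggests that enrollment had been open but does not prove that anyone was dosed. The objection stands as a limit on impact. It does not repair the formula, since SAP 6.2 keeps these arms in scope.

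A second objection is that little else depends on duration of therapy, and that is also right. Adverse event and laboratory windows run to 100 days after the last dose (SAP 7.6), person-years have their own formula (SAP 7.6.6), and hepatic summaries count subjects with abnormal values (SAP 7.6.7.1). Number of doses, cumulative dose and the drug administration listing are correct as they stand, so the right intensity could be recovered from them.

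Two stronger readings are tempting and are not supported:
- A reader might infer that on-schedule subjects would be reported as overdosed. Overdose is a separate term in Protocol 6.5, tied to an excessive and medically important dose and reportable as an SAE. A relative dose intensity category does not trigger it.
- A reader might infer that the error distorts a planned comparison of 8-week with 4-week exposure bearing on hepatotoxicity. The Protocol does describe hepatotoxicity as schedule dependent (1.4.3), but the visible SAP plans no such comparison, only descriptive statistics by group. Exposure-response modeling would use PK concentrations and be reported separately (SAP 7.7).

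**Conclusion.** The formula is wrong as written for the 8-week regimens and right for the 4-week regimens. For any subject treated every 8 weeks, duration is exactly 4 weeks short. For on-schedule dosing, dose intensity is overstated by 2.00, 1.33, 1.20, 1.14, 1.11 and 1.09 times after one to six doses. These results follow from the SAP's own formulas.

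The category result needs one assumption, that planned dose is the planned weekly dose. On that reading, on-schedule subjects with one to five doses fall in the top category, and those with six, at 109.1%, stay in the category below it.

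The consequence is limited to exposure summaries and listings; no endpoint, decision rule or safety rate changes. How much the tables would move depends on the number of subjects treated every 8 weeks, which the documents do not give and the sponsor can check. If there were none, the numerical effect is nil. The AUC(TAU) definition has the same fault, but at about 2–3% it is secondary.

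**What to change.** In SAP 7.4.1, replace 28 in the analysis derivation with the urelumab dosing interval of the regimen the subject received: 28 days for Cohorts 1, 2 and C, and 56 days for A, B and D. In the same place, define planned dose as mg per week for the regimen, so that the categories have a stated denominator. As a secondary point, define urelumab AUC(TAU) in SAP 4.2.2 over the same interval.

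SAP Table 4 and Protocol Table 3.1.5-3 must also be reconciled. The footnote marking a regimen as no longer applicable after Revised Protocol 03 is on Cohort C and absent from Cohort B in the SAP, and the reverse in the Protocol.

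The cost is a few lines of SAP text and one derivation parameter. No new data are needed and treatment does not change.

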#### **Listing:**

- Drug administration
- Number of doses, duration of therapy, cumulative dose, dose intensity, and relative dose intensity

### **7.4.2      *Modification of Study Therapy***

#### **Summary:**

The following will be provided by treatment group.

[figure not shown]
- Urelumab
  - Number (%) of subjects with dose delay and discontinuation along with the reason
  - Infusion interruptions

[figure not shown]
- ◆ Number (%) of subjects with at least one infusion interruption along with the reason\*
- ◆ Duration of interruption\*
- ◆ Number of infusion interruptions per subject
- ◆ Number (%) of subjects with at least one IV infusion rate reduction along with the reason\*
- Nivolumab
  - Number (%) of subjects with dose delay and discontinuation along with the reason
  - Infusion interruptions
    - ◆ Number (%) of subjects with at least one infusion interruption along with the reason\*
    - ◆ Duration of interruption\*
    - ◆ Number of infusion interruptions per subject
    - ◆ Number (%) of subjects with at least one IV infusion rate reduction along with the reason\*

\*More than one reason or one interruption per patient may be counted in these statistics

**Listing:**

- All relevant information on dose modification listed above

## 7.5 Efficacy

Efficacy analyses will be based on endpoints defined in [Sections 4.2.1](#) and [4.3.2](#) and performed separately on the populations of All Treated Subjects and Response Evaluable Subjects. If the majority of All Treated Subjects is included in Response Evaluable Subjects, limited efficacy analyses will be performed on the Response Evaluable Subjects (eg, ORR).

Time to event distribution (eg, PFS, OS, and DOR) will be estimated using Kaplan-Meier (K-M) method. When appropriate, the median along with 95% confidence interval (CI) will be provided using Brookmeyer and Crowley methodology. Rates at fixed timepoints (eg, PFSR at 6 months) will be derived from the K-M estimate and corresponding CI will be derived based from Greenwood's formula.

### Summary:

The following will be summarized by tumor type, treatment arm and overall.

- The ORR with corresponding 2-sided 95% CI based on the Clopper-Pearson method, along with each category of BOR.
- The DOR with median (95% CI) and range (min, max) by K-M method. The number of subjects still in response at the time of database lock will be indicated.
- The PFS and OS with median (95% CI) and range (min, max) by K-M method.
- The PF SR at specified timepoints (eg, Week 24, Week 48) by K-M method.
- The OSR (eg, Year 1, Year 2) by K-M method. If the number of subjects at risk is too small (eg, <5), OSR will not be presented.
  - Minimum survival follow-up, defined as the time between last patient last visit (LPLV) and last patient first treatment (LPFT), will be summarized by tumor type. LPLV can be replaced with database lock date depending study specific needs.
  - The currentness of follow-up, defined as the time between last OS contact (i.e., last known date alive or death date) and data cut-off date, will be summarized by treatment

group. Subjects who died before data cut-off date will automatically have zero value for currentness of follow-up. For subjects with last known date alive after data cut-off date, they will have zero value for currentness of follow-up as well. The currentness of follow-up will be categorized based on the actual data and will be described in each deliverable's DPP. An example of the categories are: 0 days, 1-30 days, 31-60 days, 61-90 days, 91-120 days, 120-150 days, 151 or more days.

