Lung cancer is the leading cause of cancer death in the US. In 2014, an estimated 224,210 new cases will be diagnosed, and 159,260 deaths are estimated to occur because of the disease accounting for 27% of all deaths due to cancer.¹ Most lung cancers (~ 80%) are non-small-cell lung cancers.¹² Of these patients, more than 65% present with locally advanced or metastatic disease.¹³ Despite treatment with platinum- and taxane-based chemotherapy, patients with metastatic NSCLC have a median survival of approximately 12 months,¹⁴ and a 5-year survival rate of approximately 15%.¹⁵ Even though there has been an increase in the number of treatment options available for patients with NSCLC, there has been little overall survival (OS) improvement from several new agents such as pemetrexed, erlotinib and bevacizumab beyond very small subpopulations. Therapeutic options for mutation wild-type NSCLC are particularly limited after failure of front-line chemotherapy. Overall, this group of patients only has an OS of about 8 months after progression from platinum agents. Once resistance to tyrosine kinase inhibitors (TKIs) occurs, the patients who have EGFR mutations or ALK translocations will have a rapid disease progression. Therefore, the majority of NSCLC cases remain a disease with high burden and unmet medical need. Anti-PD-1 therapies have recently been approved by the US FDA and the European Medicines Agency (EMA) for the treatment of advanced NSCLC. With these recent approvals, patients who relapse following treatment with anti-PD-1 or anti-PD-L1 therapies will become an important new patient category which will require new treatment options.

Head and Neck Carcinoma Squamous Cell (SCCHN)

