Head and neck cancer (HNC) is the sixth most common cancer, with a worldwide incidence of at least a half a million.^{16,17} The vast majority of cases are squamous cell carcinoma of the head and neck (SCCHN), which account for 3% to 4% of all cancers in the US.^{18,19} In 2013 in the United States, the American Cancer Society estimates 53,640 new cases are diagnosed and approximately 11,520 deaths due to this cause occur yearly.²⁰ HNCs describe malignancies of the upper aerodigestive tract which include squamous cell carcinomas (SCCHN) of the oral cavity, nasopharynx, pharynx and larynx. Smoking and tobacco products, alcohol use, and infection with human papillomavirus (HPV) are among the major risk factors, however, a shift in SCCHN epidemiology in recent decades has been observed. Tobacco- and alcohol-related disease has declined while HPV-driven malignancies have increased.²¹ Approximately 10-20% of

recurrent/metastatic SCCHN is HPV+.^{22,23} Epidemiological tracking of HPV-driven HNCs suggest that patients with HPV positive (HPV+) tumors have better response rates and survival after treatment.²⁴

Treatment of recurrent or metastatic disease involves a multimodal approach including surgery, use of cytotoxic chemotherapies such as methotrexate, organoplatinum compounds, fluorouracil (5-FU), or taxanes, combination with the biologic agent cetuximab and radiation. Despite the availability of these multimodal and novel approaches in management, prognosis has been poor for patients with disease recurrence after therapy with curative intent, with median survival for patients with locoregionally recurrent or metastatic disease, treated with palliative chemotherapy alone, being only 8–10 months.²⁵ Metastatic or recurrent SCCHN remains an area of high unmet medical need and patients who progress after treatment (refractory or platinum-resistant disease) have the worst prognosis with median OS of 3 - 4 months and 1 year survival rate of < 5%.²⁶ In conclusion, there is no effective standard of care that provides survival benefits beyond 4 - 6 months in second line platinum refractory recurrent or metastatic SCCHN. New therapeutic options are needed for this patient group.

Diffuse Large B-Cell Lymphoma (DLBCL):

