8.4.2 Efficacy Analyses

Individual best overall response (BOR), duration of response and PFS will be listed using RECIST v1.1 and IWG criteria, as appropriate. BOR outcomes will be tabulated by disease type and treatment (eg, with a column for each dose/regimen combination). The objective response rate (ORR) and PFS rate (eg, at 24 weeks) and corresponding confidence interval will be provided by tumor type and treatment. The duration of response and PFS will be estimated by Kaplan-Meier (K-M) methodology by disease type, depending on data availability. PFS rates at 24 weeks will be similarly estimated, based on K-M methodology. ORR, duration of response and PFS analyses will include subjects in the cohort expansion phase and subjects in dose escalation matching those in cohort expansion by disease type and treatment. Individual changes in the tumor burden over time may be presented graphically within a disease type. Landmark overall survival will be assessed as part of exploratory efficacy analysis, using Kaplan-Meier plots and the median (as measured using Kaplan-Meier Method) for each tumor type.

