### **2.1.2.1 Stage 1 Cohort Expansion**

Stage 1 of the expansion phase will treat 20 subjects per tumor type at the MTD or HAD as identified during dose escalation followed by continued enrollment of up to approximately 20 additional subjects (total of 40 subjects per tumor type) (Stage 2) to obtain additional safety/efficacy data for the combination. The safety, tolerability, and preliminary efficacy from Stage 1 of the cohort expansion will be evaluated per tumor type and discussed by the sponsor with investigators prior to enrolling 20 additional patients during Stage 2.

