#### **Efficacy criteria for moving to Stage 2:**

In order to enroll additional patients in Stage 2 of cohort expansion a minimum of 4 out of 20 subjects in the first stage of cohort expansion need to demonstrate an objective response to study therapy. In general, if 0 to 3 responses are observed in a given tumor specific cohort during Stage 1 of cohort expansion, Stage 2 will not be enrolled for that tumor type. Please note: Ongoing assessment of data from the initial 20 patients may be used to consider additional enrollment in that tumor type at a later date (to consider the possibility of delayed responses).

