### **6.1.4 *Survival/Long-term Period***

- Study subjects will be followed every 3 months to assess survival status
- The duration of survival follow-up will be 3 years following the first dose of study drug
- Subjects who discontinue study drug with ongoing SD, PR, or CR will continue to have tumor assessments every 12 weeks for the first year after discontinuation of study drug, and then continue to receive scans per standard of care guidelines for follow-up or at a minimum of every 6 months up to 3 years following the first dose of study drug, or until disease progression or withdrawal of consent

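### SAP 7.5 withholds the landmark overall survival rate by number at risk, so in a mature 20-subject cohort low observed rates drop out of the table because patients died

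*SAP*

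**What the plan says.** The efficacy summary in SAP 7.5 lists "The OSR (eg, Year 1, Year 2) by K-M method", by tumor type, treatment arm and overall, and adds: "If the number of subjects at risk is too small (eg, <5), OSR will not be presented". The progression-free survival rate in the same list has no such condition. Neither do the OS median with its 95% CI, the Kaplan-Meier plot of OS or the survival listing.

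On follow-up, SAP 6.1.4 states: "The duration of survival follow-up will be 3 years following the first dose of study drug", with contact every 3 months. On cohort size, SAP 2.1.2.1 states: "Stage 1 of the expansion phase will treat 20 subjects per tumor type at the MTD or HAD". Stage 2 brings a cohort to about 40, but the Stage 2 efficacy criteria begin "In general, if 0 to 3 responses are observed in a given tumor specific cohort" and go on to say that Stage 2 will then not be enrolled. The less active cohorts therefore tend to stay at 20.

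Protocol 8.4.2 sets the status of the analysis: "Landmark overall survival will be assessed as part of exploratory efficacy analysis".

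**The concern.** The number at risk at a landmark falls for two reasons. Censoring before the landmark means that the data are immature, which is a sound reason to hold back a rate. Death before the landmark is the outcome being measured, and is no reason to hold it back. The SAP rule treats the two alike.

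Follow-up runs past both example landmarks. At a mature lock, a subject not at risk at Year 1 or Year 2 has therefore died unless withdrawn or lost. Whether a cohort's rate is tabulated then depends on how many survived. A reader who compares the tabulated rates with historical landmark rates would see those that came out high enough and blanks for the rest. Because the cut of 5 is only an example, it could also be settled after the data have been seen.

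**Working it through.** **Inputs.** Cohort size n = 20, or 40 after Stage 2 (SAP 2.1.2). Example cut: fewer than 5 at risk (SAP 7.5). Follow-up: 3 years from first dose (SAP 6.1.4). Loss to follow-up, accrual time and lock date are not given, so they are assumed below, with ranges.

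**The plan's own figures.** The documents give no figure for this rule. The nearest are the Stage 1 probabilities of 4 or more responses in 20 (SAP 5.2.1): 58.9%, 89.3%, 98.4% and 99.9% at true rates of 20%, 30%, 40% and 50%, and 13.3% at 10%. The exact binomial reproduces all of them.

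**What is withheld.** With no censoring before the landmark, the number at risk equals the number alive, X, and the Kaplan-Meier rate equals X/n. The rule drops X of 4 or fewer: 4/20 = 20% or less, or 4/40 = 10% or less.

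**How often, and with what effect.** X is Binomial(n, S), where S is the true OSR.

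- P(shown) = P(X ≥ 5).
- Mean when shown = E[X/n | X ≥ 5] = (sum of x·P(X = x) for x ≥ 5) / (n·P(X ≥ 5)).
- For n = 20 and S = 20%: P(shown) = 0.370, and the mean is 2.180 / (20 × 0.3704) = 29.4%.

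| n | True OSR | Withheld | Mean when shown | Shift (points) |
|---|---|---|---|---|
| 20 | 10% | 95.7% | 26.6% | +16.6 |
| 20 | 20% | 63.0% | 29.4% | +9.4 |
| 20 | 30% | 23.8% | 34.1% | +4.1 |
| 20 | 40% | 5.1% | 41.2% | +1.2 |
| 20 | 50% | 0.6% | 50.2% | +0.2 |
| 40 | 10% | 62.9% | 15.0% | +5.0 |
| 40 | 20% | 7.6% | 20.9% | +0.9 |

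**Against the protocol's background figures.** These are historical, not rates expected on the combination.

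- Refractory SCCHN is described as "median OS of 3 - 4 months and 1 year survival rate of < 5" per cent. At a Year 1 rate of 5%, n = 20, the OSR is withheld 99.7% of the time.
- For NSCLC, "this group of patients only has an OS of about 8 months after progression from platinum agents". Read as an exponential median (an assumption), Year 1 is exp(−ln2 × 12/8) = 35.4%, withheld 11%. Year 2 is exp(−ln2 × 24/8) = 12.5%, withheld 90.5%.

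**Loss to follow-up.** This was simulated with n = 20, exponential survival and 10% to 20% lost by Year 2. For true OSR of 10% to 40%, deaths are still 80% to 96% of those no longer at risk in withheld cohorts. At a true 20% the mean when shown is 31% to 33%.

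**Lock date.** This was simulated with accrual over 1 year. At a lock 2 years after the last first dose and a true 20%, deaths are 94% of those no longer at risk in withheld cohorts. At a lock 0.5 to 1 year after it, the Year 2 OSR is withheld almost always, whatever the true rate between 20% and 60%. At a true 60%, deaths are then only 21% to 30% of those no longer at risk.

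**Precision.** With complete follow-up the standard error is √(p(1−p)/20): 8.0 points at 3/20 (withheld), 9.7 at 5/20 (shown), 11.2 at 10/20 (shown). The withheld rates are not the less precise ones. The interval is a separate matter. SAP 7.5 names Greenwood's formula and no transformation. Untransformed limits (p ± 1.96 SE) are −4.6% to 14.6% at 1/20, with lower limits of −3.1% at 2/20 and −0.6% at 3/20. At 0/20 the formula fails. Exact binomial limits are 0.1% to 24.9% at 1/20, and 0% to 1 − 0.025^(1/20) = 16.8% at 0/20.

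**The case against.** **Poor survival is not hidden.** A reader might infer that the rule conceals failing cohorts. It does not. With complete follow-up and 4 or fewer of 20 alive, at least 80% have died and the median has been reached. The median, curve and subject listing are presented unconditionally, and the rate can be recovered from them. This stands, and it limits the defect to the tabulated rate and its interval.

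**No estimate is biased.** A reader might also infer that the OS table overstates survival across tumor types. Each Kaplan-Meier estimate is sound. The shifts above are averages over hypothetical repeats in which the rate was shown, and no planned analysis averages the displayed rates. The overall summary keeps subjects from cohorts whose own rate is blank. This stands too: the set of rates on display is selected, and no more than that is shown.

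**The rule can serve maturity.** The SAP places its minimum-follow-up and currentness-of-follow-up items under the same OSR bullet, and interim reports are foreseen. At an early lock the rule does work as a maturity check. It stops doing only that once follow-up is complete.

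**Intervals near zero are awkward.** This is correct for untransformed Greenwood limits. It is a reason to change the interval, not to drop the estimate.

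**The stakes are low.** There is no formal hypothesis, and the move to Stage 2 rests on responses and safety, not OSR. The SAP's OS objective follows the secondary objectives in the text, which might suggest secondary status. A heading is blacked out in the contents at that point, so this cannot be relied on against the protocol's exploratory label.

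**Conclusion.** The concern holds as a moderate selective-reporting defect. At a mature lock (for Year 2, about 2 years or more after the last first dose), with little loss to follow-up and the example cut of 5, a 20-subject cohort has every observed OSR of 20% or less left out of the table; at 40 subjects the limit is 10%.

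The effect matters where the true OSR is about 30% or lower in a cohort of 20. It is about 1 point or less at 40% or more, and also at a true 20% with 40 subjects. In smaller groups the rule reaches higher rates: up to 4/12 = 33% at 12 subjects, and every rate below 5 subjects.

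A reader might go further and say that low rates can never be presented. The documents do not support that, since the cut is an example and the lock date is not stated. Nor do the background figures predict which cohorts will be blank. The sizes rest on binomial counts with complete follow-up; the checks with loss to follow-up point the same way.

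**What to change.** Base withholding on maturity instead of number at risk. In SAP 7.5, present the Year 1 and Year 2 OSR for each cohort with the number at risk, deaths, and number censored before the landmark. Withhold a rate only when censoring before the landmark exceeds a cut that the sponsor sets before the lock, with deaths counted as complete follow-up. This keeps the protection against immature data.

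Name an interval that behaves near zero: log-log transformed Greenwood, or exact binomial when no subject is censored before the landmark, including the case of 0 survivors.

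The cost is a few lines of SAP text and two or three counts in the table, with no change to trial conduct. The downside is that some small cohorts will show low rates with wide intervals.
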